For the following, you should find an item that the patient responded with a 2 and determine how that differed from a 1 or 3 response. Similarly, you should find an item that the patient responded with a 3 and determine how that differed from a 2 or 4 response.

You answered (2). How did you come up with that answer? What makes that a better answer than (x+1)? What makes (x) a better answer than (x-1)?

You answered (3). How did you come up with that answer? What makes that a better answer than (x+1)? What makes (x) a better answer than (x-1)?

Were there any other words in the answer choices that were confusing or hard to understand? If so, which ones?

Cognitive Interviewing Probes – Recall period

How easy or difficult was it to think about your experiences over the last 7 days? Is there a better time period for considering your experiences?

Summary Questions

Now that you have finished answering all the items, I would like to ask you a few final questions about the survey as a whole. Remember that we are only interested in improving our survey, so if something was confusing or hard to answer then make sure you tell us that, because that is exactly what we want to find out today.

- *Did you find this interview difficult?*
- *Was the survey too long?*
- *Does any one survey statement stick out in your mind as being particularly difficult for you?*
- *Is there anything else you would like us to know about this questionnaire? Do you have any suggestions for improving it for others?*

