Para lo siguiente debe encontrar un ítem para el que el paciente contestó con un 2 y determinar de qué manera difirió de una respuesta 1 o 3. También debe encontrar un ítem para el que el paciente contestó con un 3 y determinar de qué manera difirió de una respuesta 2 o 4.

Usted contestó (2). ¿Cómo llegó a esa respuesta? ¿Por qué es una mejor respuesta que (x+1)? ¿Por qué (x) es una mejor respuesta que (x-1)?

Usted contestó (3). ¿Cómo llegó a esa respuesta? ¿Por qué es una mejor respuesta que (x+1)? ¿Por qué (x) es una mejor respuesta que (x-1)?

¿Hubo algunas otras palabras en las opciones de respuesta que eran confusas o difíciles de entender? Si sí, ¿cuáles?

Sondeo de la entrevista cognitiva – Período recordatorio

¿Qué tan fácil o difícil fue pensar en sus experiencias en los últimos 7 días? ¿Existe un mejor período de tiempo para considerar sus experiencias?

Respuestas de resumen

Ahora que ha respondido todo, me gustaría hacerle un par de preguntas finales sobre la entrevista en su totalidad. Recuerde que tan solo nos interesa mejorar la encuesta, por lo que si algo le resultó confuso o difícil de contestar asegúrese de decirlo—eso es exactamente lo que queremos averiguar.

- *¿Le pareció difícil esta entrevista?*
- *¿Le pareció que la entrevista fue demasiado larga?*
- *¿Alguna afirmación en la encuesta sobresalió por ser particularmente difícil para usted?*
- *¿Hay algo más que le gustaría que supiéramos sobre este cuestionario? ¿Tiene alguna sugerencia para mejorarlo para otras personas?*

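### The Spanish script asks whether the interview was too long where the English asks whether the survey was, so the length of the Spanish measure is not directly asked

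*Protocol*

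**What the plan says.** Both interview scripts end with a short set of summary questions. In the English script (Appendix VII) the interviewer opens with "I would like to ask you a few final questions about the survey as a whole" and later asks "Was the survey too long". In the Spanish script (Appendix VIII) the opening is "me gustaría hacerle un par de preguntas finales sobre la entrevista en su totalidad" and the matching question is "Le pareció que la entrevista fue demasiado larga". Both Spanish lines name the interview; both English lines name the survey.

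Three other parts of the protocol bear on the point. The synopsis gives one session of about 45-60 minutes, and the Spanish introduction tells participants to expect an hour. The form under test has 25 items (Appendix XII). Section 2.3 gives brevity as a benefit of an index over a full quality-of-life measure, with fewer than 20 items against 40 or more as the example, and says that Round 1 in Spanish will follow the same process as the English interviews.

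**The concern.** The interview and the form are different things. The interview includes completing the form, but most of the script consists of probes about it. Someone asked whether the interview was too long is invited to judge the whole session. A yes then says little about whether 25 items are too many, and a no does not show that the form's length is acceptable.

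At stake is one intended piece of feedback on the Spanish measure. Perceived length is of some interest because brevity is part of the case for an index and because the tested form is longer than the example in Section 2.3. The ambiguity would also be hard to resolve afterwards: under Section 3.4.2 no transcripts are made and recordings are destroyed within 48 business hours, which leaves only the interviewer's notes and summary.

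**Working it through.** No arithmetic beyond counting applies. The check sets the two closing sections side by side, then searches the rest of the Spanish script for other questions on length.

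**Step 1: what each closing line refers to.**

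| Line | English (Appendix VII) | Spanish (Appendix VIII) | Same object? |
|---|---|---|---|
| Opening sentence | survey | interview | No |
| Difficulty | interview: "Did you find this interview difficult" | interview: "Le pareció difícil esta entrevista" | Yes |
| Length | survey | interview | No |
| Hardest statement | survey | survey: "Alguna afirmación en la encuesta sobresalió por ser particularmente difícil para usted" | Yes |
| Anything else, improvements | questionnaire | questionnaire: "Hay algo más que le gustaría que supiéramos sobre este cuestionario" | Yes |

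Two of the five lines differ and three match.

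**Step 2: could *entrevista* simply be a synonym for the form?** The Spanish script does not use it that way elsewhere. It uses *encuesta* for the form in the general probe on problems in answering, in the reminder that the only interest is in improving the survey, and in the question on the hardest statement. The length question also comes directly after the difficulty question, where *esta entrevista* means the interview in both languages. A participant hearing the two in sequence would most naturally take both to mean the session.

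**Step 3: is the form's length asked about anywhere else in Spanish?** The general, instruction, item-specific, response-scale and recall-period probes in Appendix VIII contain no question on it. Direct questions on the length of the measure: English 1, Spanish 0.

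**Step 4: what is still asked about the form as a whole?** The Spanish script asks how often the statements were easy to answer, whether any problem made the survey hard to answer in general, and how hard it was overall to choose a response. It asks whether all three pain items are needed. For the leisure and social items, the two enjoyment items and the two desire items, it asks whether both are needed and which one the participant would keep. It ends by inviting comments and suggestions on the questionnaire. Difficulty and redundancy are therefore covered, and length could come up unprompted in the last item.

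**The case against.** The strongest reply is that this is a small translation slip in a secondary question. The stated purpose is content validity of the Spanish measure (Sections 2.3 and 4.0). Perceived length is not an objective, an endpoint or a trigger for a further round. The item-by-item redundancy probes are more useful for shortening the form than one closing yes/no question. The sentence after the opening line points participants back to improving the survey, and the English is itself loose, since it promises questions on the survey and then asks first about the interview. The expert panel that codes the interviews (Section 5.0) could also consult the wording of the question.

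Most of this stands, and it sets the severity. It does not restore the missing question: a panel that knows the wording would know only that the answer concerns the interview.

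A reader might infer more than the documents support:

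- **That the overall burden of the Spanish form is never assessed.** Step 4 shows that overall difficulty is probed several times. Only length goes without a direct question.
- **That the whole closing section is mistranslated.** Three of the five lines match, and the difficulty question refers to the interview in both languages.
- **That a planned English-Spanish comparison is spoiled.** The protocol plans no such comparison of closing answers.
- **That the interview is some fixed multiple of the form's length.** The protocol gives no completion time for the form, so any ratio would rest on an assumed figure. The point does not need one.

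**Conclusion.** The point holds in a narrow form. The Spanish opening sentence and length question refer to the interview where the English refers to the survey. The length of the Spanish measure is therefore not directly asked, and a reply of too long may describe the session. As written, this applies to every participant, a minimum of 20 and a maximum of 40 (Section 3.3.1), but to one item only. The conclusion assumes that the Spanish script is read as printed and that the English wording shows what was intended; Section 2.3 supports the second assumption by calling for the same process. The severity is minor: one closing answer cannot be read as feedback on the form, and the content-validity work is otherwise unaffected.

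**What to change.** In Appendix VIII, replace *la entrevista* with *la encuesta* in the opening sentence of the summary questions and in the length question. Both nouns are feminine, so nothing else in either line changes. Leave the difficulty question as it is, because it already matches the English. Do not add a gloss such as the number of statements: the English has none, and it would create a new mismatch.

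The change adds no interview time. Section 7.2 requires a written amendment and approval by the IRB of each participating institution, so it is sensible to bundle it with any other script corrections. If some interviews have already used the present wording, summarise their length answers as feedback on the interview and keep them apart from later answers about the survey.

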APPENDIX IX: DEMOGRAPHIC SHEET – ENGLISH

DATE: ____/____/_____

1. Age: _____ years

2. What gender do you identify with? (Please check appropriate boxes)

- Male/Man (1)
- Female/Woman (2)
- Transgender man/Transman/Female to male (3)
- Transgender woman/Transwoman/Male to female (4)
- Genderqueer/Gender nonconforming (5)
- Something else (6)
- Decline to answer (9)

3. Do you identify as Hispanic, Latino, or Spanish?

- No (0)
- Yes (1), Nationality: _____
- Don't know (8)
- Decline to answer (9)

4. What racial group do you most identify with?

- White (1)
- Black or African American (2)
- Asian or Pacific Islander (3)
- American Indian or Alaskan Native (4)
- Other (5), please specify: _____
- Decline to answer (9)

5. What is your highest education level?

- Never attended school (1)
- Elementary school (2)
- Some high school (3)
- GED (4)
- High school graduate (5)
- Some college or technical school (6)
- College graduate (7)
- Graduate or professional school
- Decline to answer

APPENDIX X: DEMOGRAPHIC SHEET – SPANISH

FECHA: ____ / ____ / ____

1. Edad: _____ años

2. ¿Con qué género se identifica? (Seleccione las casillas correspondientes)

- Masculino/Hombre (1)
- Femenino/Mujer (2)
- Hombre transgénero/Hombre trans/Femenino a masculino (3)
- Mujer transgénero/Mujer trans/Masculino a femenino (4)
- Genderqueer (una persona que no se adscribe a distinciones convencionales de género sino que no se identifica con ninguna o que se identifica con ambas o con una combinación de masculino y femenino)/no conforme con el género (una persona cuya identidad o expresión de género actual no obedecen a las expectativas sociales basadas en el sexo que se les asignó al nacer) (5)
- Otro (6)
- Se negó a contestar

3. ¿Se identifica como hispano, latino o español?

- No (0)
- Sí (1), nacionalidad: _____
- No sabe (8)
- Se negó a contestar

4. ¿Con qué grupo racial se identifica más?

- Blanco (1)
- Negro o afroamericano (2)
- Asiático o de las islas del Pacífico (3)
- Indígena americano o nativo de Alaska (4)
- Otro: (5), por favor especifique: _____
- Se negó a contestar (9)

5. ¿Cuál es su nivel de educación más alto?

- Nunca asistió a la escuela (1)
- Escuela elemental (2)
- Algo de secundaria (3)
- GED (o diploma de equivalencia de secundaria) (4)
- Graduado de secundaria (5)
- Algo de universidad o educación técnica (6)
- Graduado de universidad (7)
- Postgrado
- Se negó a contestar

APPENDIX XI: ANCHOR HEALTH-RELATED SYMPTOM INDEX – ENGLISH

Below is a list of statements that other people diagnosed with anal HSIL (pre-cancer lesion in the anus) and treated or actively monitored have said are important. Please check the box to select your answer based on your experiences in **the past 7 days**.

PHYSICAL SYMPTOMS	Check if Not Applicable	Not at all 0	A little bit 1	Somewhat 2	Quite a bit 3	Very much 4	Difficult to Understand
1. I have anal pain							
2. I have pain other than anal pain							
3. I have pain during bowel movements							
4. I have constipation							
5. I have bleeding from the anus							
6. I have itching in or around the anus							
7. I have discharge (wetness) in my anal area							
8. I have burning sensations in the anal area							
9. I have urgency for bowel movements							
PHYSICAL IMPACTS	Check if Not Applicable	Not at all 0	A little bit 1	Somewhat 2	Quite a bit 3	Very much 4	Difficult to Understand
10. I have problems with my physical ability to move around							
11. I have problems with sitting							
12. I have problems completing daily household chores (e.g., cleaning, cooking, laundry, house maintenance)							
13. I have problems taking care of myself (e.g., bathing, dressing, shaving)							
14. I have problems participating in leisure activities (e.g., watching television, relaxing)							

15. I have problems participating in social activities (e.g., going out to eat, visiting friends)							
16. I have problems with work productivity							
PSYCHOLOGICAL SYMPTOMS	Check if Not Applicable	Not at all 0	A little bit 1	Somewhat 2	Quite a bit 3	Very much 4	Difficult to Understand
17. I have difficulty concentrating							
18. I have a decreased enjoyment of anal sexual activity							
19. I have a decreased enjoyment for any form of sexual activity other than anal sexual activity							
20. I have a decreased desire for anal sexual activity							
21. I have decreased desire for forms of sexual activity other than anal sexual activity							
22. I am worried about my condition getting worse							
23. I have anxiety							
24. I have depression							
25. I have problems with my intimate relationships							

APPENDIX XII: ANCHOR HEALTH-RELATED SYMPTOM INDEX – SPANISH

ÍNDICE DE SÍNTOMAS RELACIONADOS CON LA SALUD ANCHOR

A continuación presentamos una lista de afirmaciones que otras personas diagnosticadas con HSIL (lesión precancerosa en el ano) y que han sido tratadas o monitoreadas activamente han dicho que son importantes. Por favor seleccione la casilla con su respuesta basándose en sus experiencias en **los últimos 7 días**.

SÍNTOMAS FÍSICOS	Escoja si no aplica	Para nada 0	Un poco 1	Algo 2	Bastante 3	Muchísimo 4	Difícil de entender
1. Tengo dolor anal							
2. Tengo dolor pero no en el área anal							
3. Tengo dolor cuando entro al baño a defecar							
4. Tengo estreñimiento							
5. Tengo sangrado del ano							
6. Tengo picazón en el ano o alrededor del ano							
7. Tengo una secreción (mojado) en el área anal							
8. Tengo sensación de ardor en el área anal							
9. Siento urgencia de entrar al baño a defecar							
IMPACTOS FÍSICOS	Escoja si no aplica	Para nada 0	Un poco 1	Algo 2	Bastante 3	Muchísimo 4	Difícil de entender
10. Tengo problemas con mi capacidad física para movilizarme							
11. Tengo problemas para sentarme							
12. Tengo problemas terminando las tareas de la casa (por ej., limpiar, cocinar, hacer la colada, administrar la casa)							
13. Tengo problemas con mi arreglo personal diario (por ej., bañándome, vistiéndome, afeitándome)							
14. Tengo problemas participando en actividades de ocio (por ej., mirar televisión, relajarme)							

15. Tengo problemas participando en actividades sociales (por ej., salir a comer, visitar amigos)							
16. Tengo problemas siendo productivo en el trabajo							
SÍNTOMAS PSICOLÓGICOS	Escoja si no aplica	Para nada 0	Un poco 1	Algo 2	Bastante 3	Muchísimo 4	Difícil de entender
17. Tengo dificultad concentrándome							
18. Me ha disminuido el placer de la actividad sexual anal							
19. Me ha disminuido el placer de cualquier forma de actividad sexual diferente a la actividad sexual anal							
20. Me ha disminuido el deseo por la actividad sexual anal							
21. Me ha disminuido el deseo por formas de actividad sexual diferentes a la actividad sexual anal							
22. Me preocupa que mi enfermedad empeore							
23. Tengo ansiedad							
24. Tengo depresión							
25. Tengo problemas con mis relaciones íntimas							

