Cognitive Interviewing Probes – Instructions

Did you have any problems in understanding the instructions? If so, please describe these problems.

Below is a list of statements that other people diagnosed with anal HSIL and treated or actively monitored have said are important. Please check the box to select your answer based on your experiences in the past 7 days.

What does the word experiences mean to you as it is used in these instructions? Is there another word or phrase that you would prefer that we use?

Cognitive Interviewing Probes – Question-Specific

You were asked about PAIN as a possible symptom related to your Anal HSIL. Do you experience PAIN that is separate from ANAL PAIN or PAIN DURING BOWEL MOVEMENTS?

If so, how is the PAIN you experience different from ANAL PAIN or PAIN DURING BOWEL MOVEMENTS? Do you believe we should ask about all three types of PAIN?

What does ITCHING IN OR AROUND THE ANUS mean to you as it was used in this statement? Do you feel that ITCHING IN and ITCHING AROUND should be two separate statements?

If patient experiences DISCHARGE (WETNESS):

Which of the words DISCHARGE (WETNESS) do you prefer to describe this experience? Is there another word or phrase that you feel would better describe this experience?

What does BURNING SENSATION mean to you as it was used in this statement? Is there another word or phrase that you feel would better describe this experience?

What does PHYSICAL ABILITY TO MOVE AROUND mean to you as it was used in this statement? Is there another word or phrase that you feel would better describe this experience? If you were to choose between “moverse” and “movilizarse,” which word would you prefer?

What does PROBLEMS WITH SITTING mean to you as it was used in this statement? Is there another word or phrase that you feel would better describe this experience? Would you prefer that we use “difficulty” sitting?

What does DAILY HOUSEHOLD CHORES (CLEANING, COOKING, LAUNDRY, HOUSE MAINTENANCE) mean to you as it was used in this statement? Are there other examples that you feel would be better to describe this experience?

What does PROBLEMS TAKING CARE OF MYSELF (BATHING, DRESSING, SHAVING, ETC.) mean to you as it was used in this statement? Are there other examples that you feel would be better to describe this experience?

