¿Tuvo algún problema entendiendo las instrucciones? Si sí, por favor describa estos problemas.

*A continuación presentamos una lista de afirmaciones que otras personas diagnosticadas con HSIL (lesión precancerosa en el ano) y que han sido tratadas o monitoreadas activamente han dicho que son importantes. Por favor seleccione la casilla con su respuesta basándose en sus experiencias **en los últimos 7 días**.*

¿Qué significa para usted la palabra “experiencias” tal como se utiliza en estas instrucciones?
¿Preferiría que utilicemos alguna otra palabra o frase?

Sondeo de la entrevista cognitiva – Preguntas específicas

Le preguntaron sobre DOLOR como un síntoma posible relacionado con HSIL anal.

¿Experimenta DOLOR no vinculado con el DOLOR ANAL o DOLOR DURANTE LA DEFECACIÓN?

Si respondió que sí, ¿el DOLOR que usted siente es diferente al DOLOR ANAL o DOLOR DURANTE LA DEFECACIÓN? ¿Le parece que debemos preguntar sobre los tres tipos de DOLOR?

¿Qué quiere decir para usted PICAZÓN EN EL ANO O ALREDEDOR DEL ANO según se preguntó en esta afirmación? ¿Piensa que PICAZÓN EN y PICAZÓN ALREDEDOR deberían ser dos afirmaciones separadas?

Si el paciente experimenta SECRECIÓN (MOJADO):

¿Cuál palabra SECRECIÓN (MOJADO) prefiere para describir esta experiencia? ¿Existe otra palabra o frase que piensa que describiría mejor esta experiencia?

¿Qué significa para usted SENSACIÓN DE ARDOR según se usó en esta afirmación? ¿Existe otra palabra o frase que piensa que describiría mejor esta experiencia?

¿Qué significa para usted LA CAPACIDAD FÍSICA PARA MOVILIZARSE en esta afirmación? ¿Existe otra palabra o frase que piensa que describiría mejor esta experiencia? Si tuviera que elegir entre “moverse” o “movilizarse”, ¿cuál palabra elegiría?

¿Qué significa para usted TENER PROBLEMAS PARA SENTARSE en esta afirmación? ¿Existe otra palabra o frase que piensa que describiría mejor esta experiencia? ¿Preferiría que se usara la frase “dificultad para sentarse”?

¿Qué significa para usted TAREAS DE LA CASA DIARIAS (LIMPIAR, COCINAR, HACER LA COLADA, LLEVAR LA CASA) según se usó en esta afirmación? ¿Hay otros ejemplos que piensa que funcionarían mejor para describir esta experiencia?

¿Qué significa para usted PROBLEMAS PERSONALES DIARIOS (BAÑÁNDOSE, VISTIÉNDOSE, AFEITÁNDOSE, ETC.) según se usó en esta afirmación? ¿Hay otros ejemplos que piensa que funcionarían mejor para describir esta experiencia?

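### Spanish item 2, read literally, denies anal-area pain where the English does not, and the Spanish pain follow-up has lost its open 'how', which weakens detection of the problem

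*Protocol*

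**What the plan says.** The English index (Protocol, Appendix XI) and the English interview script (Appendix VII) give item 2 as "I have pain other than anal pain". The Spanish index (Appendix XII) and the Spanish script (Appendix VIII) both give it as "Tengo dolor pero no en el área anal". It directly follows item 1, "Tengo dolor anal". Each item is rated 0 to 4, with separate columns for not applicable and for difficulty in understanding.

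On the sexual-activity items, the same translation deals with the English *other than* differently. Item 19 reads "Me ha disminuido el placer de cualquier forma de actividad sexual diferente a la actividad sexual anal", and item 21 uses the plural of the same construction.

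Among the question-specific probes, both scripts first ask whether the participant has pain separate from anal pain and pain on defecation. The English follow-up is "If so, how is the PAIN you experience different from ANAL PAIN or PAIN DURING BOWEL MOVEMENTS". The Spanish follow-up is "Si respondió que sí, ¿el DOLOR que usted siente es diferente al DOLOR ANAL o DOLOR DURANTE LA DEFECACIÓN". Both scripts then ask whether all three kinds of pain should be asked about.

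Sections 2.3 and 4.0 state that the interviews are meant to establish content validity in Spanish. Round 1 has 20 interviews. Section 2.3 makes Rounds 2 and 3, of up to 10 each, conditional on need.

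**The concern.** A cognitive-interview study of a translation has to start from items that ask the same thing as the source, or else has to notice when they do not. Item 2 is open to doubt on both counts. Its Spanish wording can turn a question about an additional pain into a statement that excludes anal-area pain. The follow-up that would have had participants describe the difference between their pains in their own words has been closed.

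If respondents with both pains take the Spanish literally, their non-anal pain is recorded too low or as not applicable, and item 2 is not equivalent across the two languages. If the interviews do not bring this out, the wording could be carried into the final Spanish measure, which Section 7.1 says will be implemented in ANCHOR for validity and reliability testing.

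**Working it through.** No sample size, error rate or estimate is involved, so the check is a side-by-side reading.

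**Step 1: what item 2 asks.** The English describes a kind of pain, any that is not anal pain, and is silent on whether anal pain is also present. The Spanish states that there is pain and adds *pero no en el área anal*, that is, *but not in the anal area*. Taken through the four possible respondents, with *yes* meaning a rating above 0:

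| Respondent has | English items 1 / 2 | Spanish items 1 / 2, literal reading | Spanish items 1 / 2, loose reading (pain elsewhere) |
|---|---|---|---|
| Neither pain | no / no | no / no | no / no |
| Anal pain only | yes / no | yes / no | yes / no |
| Other pain only | no / yes | no / yes | no / yes |
| Both | yes / yes | yes / **no or not applicable** | yes / yes |

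The versions part only in the last row, and only on the literal reading. There, endorsing item 1 makes the second clause of item 2 false.

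**Step 2: is this just how the translation expresses *other than*?** No. Items 19 and 21 contain the same English phrase and use *diferente a* and *diferentes a*. That construction says nothing about the anal counterpart, so those items can be endorsed together with items 18 and 20. Item 2 departs from the translation's own pattern.

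**Step 3: what the follow-up elicits.** The English asks "how is the PAIN you experience different from ANAL PAIN or PAIN DURING BOWEL MOVEMENTS", which needs a description. The Spanish asks whether "el DOLOR que usted siente es diferente al DOLOR ANAL o DOLOR DURANTE LA DEFECACIÓN", which can be answered yes or no. It is put only to someone who has just said they have pain not linked to the other two, so a yes adds almost nothing. The loss is specific to pain: the Spanish probes comparing the sexual-activity items keep the open form *¿En qué se diferencia…?*

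**Step 4: what detection remains.** Take a participant with both pains who rates Spanish item 2 as 0 because of the wording.

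- All 25 answers are read back and recorded, so the 0 is on file.
- The first pain probe is worded neutrally and independently of item 2. This participant should answer yes to it, which conflicts with the recorded 0.
- The question about the three kinds of pain may prompt comment.
- The difficulty column leads to an open review, but only if the participant ticks it. A sentence that is easy to read but means the wrong thing need not be ticked.
- The closing questions invite suggestions.

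The discrepancy can therefore be seen. However, the script does not tell the interviewer to compare the probe answer with the item 2 rating, and no pain probe repeats item 2's wording. Under Section 3.4.2 there are no transcripts and recordings are destroyed within 48 business hours, so a cue missed in the notes cannot be revisited for long.

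**The case against.** The strongest reply is that the literal reading is not the only one. Coming straight after an item on anal pain, Spanish item 2 can be taken simply to locate the pain being rated, namely elsewhere. Respondents who read it so answer as in English. This stands: the defect creates a risk of under-reporting, not a certain wrong answer.

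A reader might infer that the item scores too low in the participants with the most pain, and might support this from the surgical study in Section 2.3, where 16 of 29 patients reported uncontrolled pain. The documents do not support that. The figure concerns pain after the procedure, and the same paragraph says most of it came with bowel movements, which is nearer to items 1 and 3. It gives no frequency of non-anal pain or of both pains together. The group at risk is people with two kinds of pain, not those with the most severe pain.

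A reader might also infer that this wording goes into ANCHOR as it stands. The Synopsis treats it as an initial Spanish draft for feedback, with revised items retested, and Section 7.1 sends only the resulting final measure to ANCHOR. This study compares no scores between languages.

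It is also fair to say that finding such faults is what the interviews are for, and that the routes listed in the working survive. Detection is weakened, not removed. Nor is the absence of a question asking participants to paraphrase item 2 a translation fault, since the English script has none either. What the objection does not answer is that both departures from the English can be seen now, and that knowingly testing a wording fault uses up part of a small set of interviews.

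**Conclusion.** The point holds in limited form. Spanish item 2 is not equivalent to its English source: read literally it denies anal-area pain, so a respondent with both anal and other pain may under-report it. The Spanish pain follow-up has become a yes/no question, which makes the interviews less likely to show this.

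The size cannot be stated. It depends on the proportion of participants with both pains and on the proportion of those who read the item literally, and the documents give neither. The 0 to 4 range caps the shift for one person on one item at 4 points, but that is only the range of the item, not an expected effect. Respondents with one pain or none are unaffected.

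The conclusion rests on the plain meaning of the Spanish clause and on the contrast with items 19 and 21. It needs no assumption about prevalence. It does not show that ANCHOR scores will be biased, or that the fault would go unnoticed. Correction before Round 1 is still warranted, because the fault lies in the instrument and script on which the claim of Spanish content validity depends, and the correction is small.

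**What to change.** Before Round 1:

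1. Reword Spanish item 2 in Appendices VIII and XII so that it can be endorsed together with item 1, following the pattern of items 19 and 21. For example: *Tengo dolor diferente al dolor anal*. This is preferable to a phrase such as *otro tipo de dolor*, which may presuppose a first pain and so trouble someone whose only pain is not anal.
2. Restore the open follow-up in Appendix VIII, matching the Spanish sexual-activity probes. For example: *¿En qué se diferencia el DOLOR que usted siente del DOLOR ANAL o del DOLOR DURANTE LA DEFECACIÓN?*
3. Optionally, ask participants to say in their own words what item 2 means. This goes beyond the English script and is not needed to correct the translation.

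The cost is one line in each of two appendices for the item and one line in the Spanish script for the probe, with slightly longer answers in interviews where another pain is reported. The downside is that the translation on file must be reissued.

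### Spanish item 12 matches neither its English source nor its own probe, and the item 11 probe does not test whether the Spanish verb is read too narrowly

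*Protocol*

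**What the plan says.** Section 2.3 and Section 4.0 state that the cognitive interviews are to establish the content validity of the Spanish measure. The English instrument is Appendix XI and the Spanish one Appendix XII. The interview scripts, each with its own copy of the items, are Appendix VII (English) and Appendix VIII (Spanish).

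Item 12 in English reads "I have problems completing daily household chores (e.g., cleaning, cooking, laundry, house maintenance". In Appendix XII it reads "Tengo problemas terminando las tareas de la casa (por ej., limpiar, cocinar, hacer la colada, administrar la casa". Appendix VIII prints the same Spanish stem but ends the examples with *llevar la casa*. Its probe for this item also has *llevar la casa*, and adds *diarias*.

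Item 11 in English reads "I have problems with sitting". Both Spanish appendices have "Tengo problemas para sentarme". The Spanish probe asks what the phrase means, whether another word or phrase would be better, and finally "Preferiría que se usara la frase “dificultad para sentarse". The English probe ends in the same way: "Would you prefer that we use “difficulty” sitting".

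**The concern.** The items are both what the study produces and what it shows to participants. If an item differs from its source before the first interview, the interviews test the wrong text. If an item differs from its own probe, participants are asked the meaning of words that they did not read.

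Participants must have limited English under Section 3.1, and the script does not show them the English items. They can say whether a Spanish phrase is clear. They are poorly placed to say that something in the English has been lost. *Administrar la casa* is clear Spanish, so an item can be well understood and still ask something different. The protocol describes the translation as already made and sets out no separate step comparing it with the English. Rounds 2 and 3 follow only if needed, so a shift that Round 1 does not bring out may not be looked at again.

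**Working it through.** No arithmetic applies and the plan gives no figure to reproduce. The check is a word-by-word comparison.

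**Item 12**

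| Place | Word for daily | Last example |
|---|---|---|
| Appendix XI item (English) | yes | house maintenance |
| Appendix VII item and probe (English) | yes | house maintenance |
| Appendix XII item (Spanish) | none | *administrar la casa* |
| Appendix VIII item (Spanish) | none | *llevar la casa* |
| Appendix VIII probe (Spanish) | *diarias* | *llevar la casa* |

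1. In English, the instrument, the script and the probe agree on both features. In Spanish, the three places show three different combinations.
2. The source examples are "e.g., cleaning, cooking, laundry, house maintenance" and the Appendix XII examples are "por ej., limpiar, cocinar, hacer la colada, administrar la casa". The first three match. The fourth does not: physical upkeep of the home has become management of the household, in a block headed as physical impacts. *Llevar la casa* has the same fault, so making the appendices agree on either existing version would leave house maintenance untranslated.
3. The probe asks what the phrase means as used in the statement, yet *diarias* is not in the statement. Spanish item 13 has *diario* where its English source has no such word. This suggests a drafting slip rather than deliberate adaptation, but does not prove it.
4. Appendix VI sends participants a copy of the index to have at hand, without saying which printing. If it is the Appendix XII text, they would read *administrar la casa* and be asked about *llevar la casa*.

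**Item 11**

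1. English *sitting* covers both sitting down and being seated. Spanish *sentarse* literally denotes the act of sitting down; being seated is *estar sentado/a*.
2. The only alternative that the probe offers changes *problemas* to *dificultad* and keeps the verb. The contrast between the two meanings is never put to the participant.
3. The script already has a device for this. For item 10 it asks participants to choose between *moverse* and *movilizarse*.

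The glosses on the Spanish are ordinary usage, not statements in the protocol. The study's translators should confirm them.

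**The case against.** The strongest reply is that this is text under test. The Synopsis calls it an initial draft and provides for revised items in later rounds. The item 11 probe does ask openly what the phrase means and whether another would serve better, so a participant whose trouble is staying seated has an opening to say so. The item 12 probe asks for better examples and puts *diarias* to the participant. Section 5.0 has an expert panel code the interviews, and nothing stops that panel from comparing a paraphrase with the English. In item 12 the stem and three of the four examples are intact.

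Most of this stands for item 11. Some respondents will read *sentarse* broadly, the probe follows its English model, and it would be wrong to say that the interviews cannot reveal a narrow reading. They do not target it, which is a smaller complaint.

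Less of it stands for item 12. Interviews are for finding what the drafters cannot see, whereas a mismatch between an item, its probe and the instrument is visible on the page. Having *diarias* in the probe does not repair the item; it means that the reply concerns a different phrase.

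A reader might also infer that 2 of the 7 physical-impact items (items 10 to 16; 2/7 = 29%) are biased, and that item 11 will be under-reported because someone who can sit down but not stay seated would score 0. The documents do not support this. The fraction counts items and measures no bias. Nothing in the protocol shows how respondents read item 11. This protocol plans no comparison of English with Spanish scores, and validity and reliability testing is left to ANCHOR.

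**Conclusion.** Item 12 needs correcting before Round 1. It departs from its English source on two features, from its own probe on one, and Appendix VIII departs from Appendix XII on one. Item 11 needs only a sharper probe: its wording may be read more narrowly than the English, but whether it is remains an open question that the interviews can answer.

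The conclusion rests on the printed text and on ordinary meanings of the Spanish words. It affects no sample size or error rate, and no size or direction of score bias can be given. What is at stake is whether the planned 20 Round 1 interviews test item 12 in a form already known to differ from its source.

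**What to change.** For item 12, use one wording in the Appendix VIII item, the Appendix VIII probe and Appendix XII. It should restore daily and render house maintenance, for example *las tareas diarias de la casa (por ej., limpiar, cocinar, hacer la colada, mantenimiento de la casa)*, subject to the translators' confirmation.

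For item 11, leave the wording unchanged for Round 1 and add one question to the probe asking participants to choose between *sentarse* and *estar sentado/a*, in the form already used for item 10. Rewording the item now to name both sitting down and staying seated would put two actions in one statement, a structure that the script itself questions for itching in and around the anus.

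The cost is one item and its probe reconciled across two appendices, and one short question added to a session of about 45 to 60 minutes. Under Section 7.2 this needs a written amendment and the approvals named there.
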